- The subject is to be informed that use of prophylactic antipyretic/pain medication, is not permitted on the day of study drug administration. If antipyretic/pain medication is used after study drug dosing, and if clinically appropriate in the judgement of the Investigator, acetaminophen is preferred over other non-steroidal anti-inflammatory drugs.
- Prior and concomitant medications will be reviewed if the subjects took any during the active study period.
- The subject will be asked to bring the completed Diary to the next visit.
- The subject will be reminded that study staff may contact them to obtain additional information on events entered into the Solicited Symptom Diary.
- Source documents will be completed.
- The Investigator or appropriately qualified designee will review the Diary following vaccination, to evaluate subject compliance and as part of the ongoing safety review. Daily review is optimal during the active Diary period. Any solicited symptom marked as Grade 3 should be specifically reviewed with the subject to ensure they meet the

detailed solicited AE grading criteria in ([Table 10](#)) and to evaluate for potential alternative etiology.

- An appointment will be scheduled for the subject to return for the next study visit.
- The Investigator or an authorized designee completes the eCRFs and an unblinded dispenser/administrator will update the investigational product accountability records.
- The subjects will be contacted by phone between site visits on Day 15 to monitor for safety as specified in the SoA ([Table 1](#)). If the study personnel are unable to contact the subject with 3 attempts, the study personnel will follow instructions given in [Section 5.4](#).

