7.1.5 Unscheduled Visit

At the discretion of PI and/or per subject request to evaluate any of the expected reactogenicity symptoms or any unexpected symptoms of concern, a contact must occur as soon as possible between the subject and the Investigator, or a medically qualified member of the study site staff, to assess if an unscheduled visit is required.

This contact will be recorded in the subject's eCRF. If the subject is unable to attend the unscheduled visit, any ongoing reactions must be assessed at the next scheduled visit. Reactogenicity events should be assessed by the Investigator or a medically qualified member of the site staff, such as a study physician or a study nurse, as applicable, to the Investigator's local practice, who will:

- Measure oral temperature.
- Measure the subject's pulse rate (after five minutes of sitting).
- Measure the subject's blood pressure (after five minutes of sitting).
- Assess any events (specify the events of interest) that are present, in accordance with the reactogenicity grading scale.
- Perform a symptom focused physical examination.
- Ask the subject if she attended an emergency room visit or was hospitalized.
- Complete the source documents.
- The Investigator or an authorized designee will complete the eCRF.

The subject will be instructed to contact the site to report any significant illness, AEs, or hospitalization that occurs during the study period.

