14. QUALITY CONTROL AND QUALITY ASSURANCE

14.1 Early Safety Data Review AND/OR Committee

Subject safety will be continuously monitored by the Sponsor or designee, which includes safety signal detection during the study.

All safety data collected will be summarized and reviewed by the sponsor's internal/external safety monitoring committee for agreement of next steps.

In particular, data will be reviewed by the sponsor for identification of the following events that would potentially contribute to a requirement to [pause/stop] the study.

- One or more subjects experiences a treatment-related serious adverse event (SAE) of any grade
- Two or more subjects experience the same treatment-related grade ≥ 3 solicited symptom within one week following vaccination.
- Two or more subjects experience the same treatment-related unsolicited grade "severe" AE between Day 1 and Day 29 (Active Period).

Enrollment will be paused during the review. If a pausing/stopping rule is met, a decision will be made, based on the review, as to whether enrollment in the study will be allowed to resume. If no dose-related toxicities are observed, and upon the recommendation of the SMC following review of safety data, enrollment of the remaining subjects will be initiated.

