Appendix 3: Adverse Events Grading

Grading of Solicited Adverse Events

Subjects should be instructed to rate Solicited Symptoms of Reactogenicity that are collected within their Solicited Symptom Diary based on the severity scale presented in [Table 10](#).

Table 10 Grading of Solicited Symptoms of Reactogenicity

Symptom	Grading				
	Normal 0	Mild Grade 1	Moderate Grade 2	Severe Grade 3	Life Threatening Grade 4
Fever (oral temp)	< 100.4°F (< 38.0°C)	100.4 – 101.1°F (38.0 – 38.4°C)	101.2 – 102.0°F (38.5 – 38.9°C)	102.1 – 104°F (39.0 – 40°C)	> 104.0°F (>40°C)
Headache	None	No interference with activity	Repeated use of nonnarcotic pain reliever > 24 hours or some interference with activity	Significant; any use of narcotic pain reliever or prevents daily activity	ER visit or hospitalization
Myalgia (muscle pain)	None	AE easily tolerated, causing minimal discomfort and does not interfere with everyday activities ^a	Adverse event sufficiently discomforting to interfere with everyday activities	Adverse event prevents normal everyday activities or requires medical advice	ER visit or hospitalization
Abdominal Pain	None	No interference with activity	Some interference with activity not requiring medical intervention	Prevents daily activity and requires medical intervention	ER visit or hospitalization
Anorexia	None	No interference with activity	Some interference with activity not requiring medical intervention	Prevents daily activity and requires medical intervention	ER visit or hospitalization
Nausea	None	No interference with activity or 1 to 2 episodes	Some interference with activity or >2 episodes	Prevents daily activity, requires outpatient IV hydration	ER visit or hospitalization for hypotensive shock
Vomiting	None	No interference with activity or 24 hours	Some interference with activity or 24 hours	Prevents daily activity, requires outpatient IV hydration	ER visit or hospitalization for hypotensive shock
Diarrhea	None	2 to 3 loose stools or < 400 gms/24 hours	4–5 stools or 400 to 800 gms/24 hours	6 or more watery stools or > 800gms/24 hours or requires outpatient IV hydration	ER visit or hospitalization
Malaise/ Fatigue	None	No interference with activity	Some interference with activity	Significant; prevents daily activity	ER visit or hospitalization

^a Everyday activity include attendance at work, school, and usual habits of the subjects.**Appendix 4: Contraceptive Guidance and Collection of Pregnancy Information****Definitions***Postmenopausal female:*

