#### 13.1 Solicited Symptoms of Reactogenicity

Solicited symptoms are predefined signs and symptoms of reactogenicity for which the subject is specifically questioned, and which are noted by the subject in their Solicited Symptom Diary, including:

- Fever (any temperature 100.4°F or higher)
- Headache
- Myalgia (muscle pain)
- Abdominal Pain
- Anorexia (defined and not eating)
- Nausea
- Vomiting
- Diarrhoea
- Malaise/Fatigue

Subjects will utilize a Solicited Symptom Diary issued on the day of the vaccination to record solicited symptom daily for one week (from Day 1 to Day 8) following that administration. After Day 8 solicited symptoms will be captured as unsolicited Adverse Events as described in [section 13.2](#) with Day 8 as date of onset.

The count and percentage of subjects and the associated Clopper-Pearson 95% CIs reporting at least one solicited symptom during 8 days after vaccine administration (the 8 days include Day 1) will be summarized for each dose and presented by severity and cumulatively across severity levels as listed below:

- Grade 1 Solicited Symptoms
- Grade 2 Solicited Symptoms
- Grade 3 Solicited Symptoms
- Grade 4 Solicited Symptoms

where Grade 1 is mild, Grade 2 is moderate, Grade 3 is Severe, and Grade 4 is Potentially Life threatening as defined in Table 10 “Grading of Solicited Symptoms of Reactogenicity”.

Missing reactogenicity Diary data will not be imputed.

All the solicited symptoms collected during the active period of the study will also be presented for each treatment arm, study day, by severity in by-subject listing.

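### Protocol 7.1.2 requires a Table 10 check of diary symptoms marked Grade 3 but not of those marked lower, so an under-marked severe reaction has no required route into the Grade ≥3 count

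*Protocol*

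**What the plan says.** The subject assigns the grade. Protocol Appendix 3 states: "Subjects should be instructed to rate Solicited Symptoms of Reactogenicity that are collected within their Solicited Symptom Diary", using the Table 10 scale.

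Protocol 7.1.2 describes what the site does with the diary. The general instruction is "The Investigator or appropriately qualified designee will review the Diary following vaccination, to evaluate subject compliance and as part of the ongoing safety review". The one instruction to verify a grade follows: "Any solicited symptom marked as Grade 3 should be specifically reviewed with the subject to ensure they meet the" criteria of Table 10, "and to evaluate for potential alternative etiology". It names Grade 3 and no other grade.

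Two other routes exist. Protocol 7.1.2 says that "study staff may contact them to obtain additional information on events entered into the Solicited Symptom Diary". Protocol 7.1.5 has staff at an unscheduled visit do the following: "Assess any events (specify the events of interest) that are present, in accordance with the reactogenicity grading scale".

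The grade is used in two places. Severity of solicited symptoms over one week is a primary safety endpoint (Protocol 3.2.1). SAP 13.1 has it "summarized for each dose and presented by severity and cumulatively across severity levels as listed below", with Clopper-Pearson 95% intervals. Protocol 14.1 lists among the pause/stop events: "Two or more subjects experience the same treatment-related grade" 3 or higher solicited symptom in the week after dosing.

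Neither document says whether the review replaces the marked grade, or whether the marked or the reviewed grade feeds the SAP 13.1 tables or the trigger.

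**The concern.** Lay self-grading can err in either direction. Several Table 10 boundaries rest on facts that a subject may not connect with a grade: any narcotic pain reliever puts headache at Grade 3, a need for medical advice puts myalgia at Grade 3, and six watery stools or a temperature of 39.0°C do the same for diarrhea and fever. A woman who marks such an event Grade 2 meets no required check. A woman who marks Grade 3 without meeting the criteria does.

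If over-marks are corrected and under-marks are left, the reported Grade ≥3 frequency falls below the true one. The study is descriptive, so absolute severe-reaction rates by dose are the safety result itself. The trigger needs only two women with the same symptom, so one missed grade can decide whether it is met.

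**Working it through.** The plan gives no figure to reproduce: sample size was set by clinical judgement (Protocol 11.1) and no rate of severe reactogenicity is assumed.

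**Direction.** Suppose grades are changed on the Grade 3 review alone.
- A Grade 3 mark that meets Table 10 stays in the ≥3 count.
- A Grade 3 mark that proves to be Grade 4 stays in the ≥3 count.
- A Grade 3 mark that fails Table 10 leaves it.
- A Grade 0 to 2 mark that meets a Grade 3 criterion is not looked at and cannot enter it.

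The count can therefore only stay or fall relative to the diary as marked.

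**Size, as an illustration.** From the documents: 30 + 30 = 60 vaccinated women and a threshold of two. Assumed:
- p, the true rate of one treatment-related Grade ≥3 symptom;
- u, the share of true Grade ≥3 events marked lower;
- o, the share of other women wrongly marking Grade 3.

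The rate q that is counted is:
- diary as marked: q = p(1 − u) + (1 − p)o
- one-way review (false Grade 3 marks removed, missed ones not recovered): q = p(1 − u)
- two-way review: q = p

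P(two or more of 60) = 1 − (1 − q)^60 − 60q(1 − q)^59.

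At p = 5%, two-way: 1 − 0.0461 − 0.1455 = 0.808. At p = 5% and u = 50%, one-way, q = 0.025: 1 − 0.2189 − 0.3368 = 0.444.

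| True rate p | One-way, u = 10% | One-way, u = 25% | One-way, u = 50% | Two-way |
|---|---|---|---|---|
| 1% | 0.102 | 0.075 | 0.037 | 0.121 |
| 2% | 0.294 | 0.227 | 0.121 | 0.338 |
| 5% | 0.758 | 0.663 | 0.444 | 0.808 |

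With u = 0 the one-way and two-way figures are equal at every p. The shortfall comes only from under-marked severe events.

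**Over-marking.** At p = 2%, u = 25%, o = 1%, the marked rate is 0.02 × 0.75 + 0.98 × 0.01 = 0.0248. The chance of two or more is 0.440 as marked, 0.227 after one-way review and 0.338 after two-way review. Here the raw diary overstates the truth and the one-way review understates it.

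**Severity table.** At p = 5% the expected reported rate under one-way review is 4.5% (u = 10%) to 2.5% (u = 50%). In an arm of 30, one woman is 3.3 percentage points. The Clopper-Pearson interval for 1 of 30 is 0.1% to 17.2%, and for 2 of 30 it is 0.8% to 22.1%.

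**The case against.** The strongest reply is that upward correction is already possible. The whole diary is reviewed, daily review is described as optimal, staff may query any entry, and an unscheduled visit grades whatever is present. Concomitant medication is recorded with its reason (Protocol 6.10), a study thermometer is provided (Protocol 7.1.1), and the Medical Monitor reviews cumulative safety data (Protocol 10.1). This stands in part. A reader might infer that grades can only be revised downward, and the documents do not say so. None of these routes, however, requires an under-marked entry to be compared with Table 10.

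Four other stronger readings are tempting and unsupported.
- **That re-grading takes place.** The text describes a review. Table 7 gives the diary as the reporting method for solicited events, and Protocol 13.2 says corrections must not hide the original entry. Replacement of the grade is an inference, so the direction argument is conditional on it.
- **That every Grade 3 mark removed is a lost severe event.** An entry that fails Table 10 was not Grade 3, and its removal is a correction. A calculation that only takes Grade 3 marks away does not measure the bias.
- **That an arm is favoured.** Subjects and site personnel are blinded (Protocol 6.7.2), so the effect should fall on all arms.
- **That finding another cause lowers the grade.** Protocol 9.3 asks for causality on every adverse event. Nothing links an alternative cause to a change of grade.

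It might also seem safer to make the unreviewed self-grade the main result. That would keep false Grade 3 marks in the table and leave any two-way check out of it.

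**Conclusion.** The required verification is asymmetric around Grade 3. If it changes grades, the Grade ≥3 count can only hold or fall. Where severe events are under-marked, the absolute severe-reactogenicity rate and the trigger count are then biased low in all arms.

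The size is unknown because the documents give no under-marking share. At a true 5% among 60 vaccinees, with 10% to 50% of severe events under-marked, the chance of two or more is 76% to 44% under one-way review, against 81% under two-way review. With no under-marking the difference is zero. These figures assume independent women, a single symptom, and all 60 counted at the end. In practice the trigger is watched as enrolment proceeds.

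For the per-arm severity tables the likely shift is small beside the sampling uncertainty at 30 women. This is a cheap improvement: it does not invalidate the safety analysis.

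**What to change.** **Protocol 7.1.2.** Apply the Table 10 check to every diary entry whose recorded temperature, stool count, medication use or care-seeking meets a different grade from the one marked, in either direction.

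**SAP 13.1.** State that the grade after this two-way review feeds the severity tables and the Protocol 14.1 trigger, and list the grade as marked beside it. Listing 16.2.7.2 (diary card with severity grading) is a natural place.

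The Table 10 criteria and the trigger's threshold are unchanged.

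**Cost.** One protocol sentence, one SAP sentence, one more data field, and a few more entries to check at Day 8. Thermometer readings, concomitant medication and the diary are already collected. The diary form is not among the documents, so confirm that it records the underlying facts, such as stool count, as well as the grade.

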7.1.3. Procedure to be followed during follow-up period (Day 30 to Day 365)

- Verify understanding of and compliance with protocol requirements for contraception (see [Appendix 4](#)).
- Subjects will return to the site on Day 60 and Day 180:
 1. A blood sample will be collected for immunogenicity assessment on D180 as specified in the SoA ([Table 1](#)).
 2. Nasal and saliva samples will be collected for immunogenicity assessment on Day 60 and Day 180 as specified in the SoA ([Table 1](#)).
 3. Ascertain if the subject is still breastfeeding. If they are then ensure the subject has also collected breastmilk sample and infant stool sample during the timepoints specified in the SoA ([Table 1](#)), if not then remind the subject. Review with the subject how the collection was done and if the samples were properly stored.
 4. Collect the most current infant vaccine record on Day 60 or any time after.
- Collect and record SAEs, AESIs and NOCIs.
- Complete the source documents.
- The Investigator or an authorized designee completes the eCRFs.
- Ask the subject to contact the site staff or Investigator if an adverse event (e.g., doctor's visit, emergency room visit) or hospitalization occurs.
- The subjects will be contacted by phone between site visits on Day 120, Day 240, Day 300, and Day 365 to monitor for safety as specified in the SoA ([Table 1](#)). If the study personnel are unable to contact the subject with 3 attempts, the study personnel will follow instructions given in [Section 5.4](#).

7.1.4 Follow-up of Subjects with Related AEs or with AEs that Led to Study Discontinuation

Unless the subject refuses further contact, each subject who experiences an AE (whether serious or non-serious) during the study must be followed until the condition resolves, becomes stable, or

becomes chronic (even after the end of the subject's participation in the study) if either of the following is true.

- The AE is considered by the Investigator to be related to the product administered.
- The AE caused the discontinuation of the subject from the study.

7.1.5 Unscheduled Visit

At the discretion of PI and/or per subject request to evaluate any of the expected reactogenicity symptoms or any unexpected symptoms of concern, a contact must occur as soon as possible between the subject and the Investigator, or a medically qualified member of the study site staff, to assess if an unscheduled visit is required.

This contact will be recorded in the subject's eCRF. If the subject is unable to attend the unscheduled visit, any ongoing reactions must be assessed at the next scheduled visit. Reactogenicity events should be assessed by the Investigator or a medically qualified member of the site staff, such as a study physician or a study nurse, as applicable, to the Investigator's local practice, who will:

- Measure oral temperature.
- Measure the subject's pulse rate (after five minutes of sitting).
- Measure the subject's blood pressure (after five minutes of sitting).
- Assess any events (specify the events of interest) that are present, in accordance with the reactogenicity grading scale.
- Perform a symptom focused physical examination.
- Ask the subject if she attended an emergency room visit or was hospitalized.
- Complete the source documents.
- The Investigator or an authorized designee will complete the eCRF.

The subject will be instructed to contact the site to report any significant illness, AEs, or hospitalization that occurs during the study period.

7.2. Management of Blood/Saliva/Nasal/Breastmilk/Infant Fecal Samples

7.2.1. Blood/Saliva/Nasal/Breastmilk/Infant Fecal Sample Collection

Blood / saliva samples for the assessment of immunogenicity will be collected from the subjects as specified in the SoA ([Table 1](#)). Sample collection, storage, and shipping information can be found in the General and Immunogenicity Laboratory Manuals.

7.2.2 Blood/Saliva/Nasal/Breastmilk/Infant Fecal Sample Preparation

Detailed instructions on how to prepare blood samples for assessment of immune response are contained in the study specific Laboratory Manual provided to the site.

7.2.3 Blood/Saliva/Nasal/Breastmilk/Infant Fecal Sample Storage and Shipment

Detailed instructions on blood sample storage and shipment are contained in the study specific Laboratory Manual provided to the site.

7.2.4 Future Use of Stored Specimens and Data

The current trial is an early phase study in which Vaxart's goal is to understand the mechanism of action of the oral NoV vaccine in the prevention of NoV illness, it is important to have samples available for the full characterization of the vaccine. The Sponsor is planning to store blood, saliva, nasal, breastmilk, and infant stool samples post the completion of the study for possible future testing towards the development of a NoV vaccine. This testing includes evaluation of serum antibody titers to NoV and cell-mediated immune responses to NoV. At this time, the exact tests are not known but this will help to further understand how the oral NoV vaccine works in the body and in the prevention of NoV illness. Other immunological assays may be performed to further elucidate the response to our vaccine. These may include cloning the antibodies that are induced following immunization. All samples will use subject identifiers that are coded and will not include subject initials or demographic information. Only Vaxart staff will have access to the samples and data; they will be responsible for providing access to the samples as needed for assays. Samples will be stored at Vaxart or Vaxart's designee in a secured, access-controlled location for at least 05 years after the last license approval in the relevant market areas has been obtained for the vaccine being tested. Samples may be shared with collaborating researchers, but only in relationship to the NoV program. Any data developed externally will only be displayed in a deidentified form as authorized by Vaxart.

8. TRIAL ASSESSMENTS AND PROCEDURES

Immediate safety concerns should be discussed with the Sponsor immediately upon occurrence or awareness to determine if the subject should continue or discontinue study drug.

Adherence to the study design requirements, including those specified in the SoA is essential and required for study conduct.

All screening evaluations must be completed and reviewed to confirm that potential subjects meet all eligibility criteria. The Investigator will maintain a screening log to record details of all subjects screened and to confirm eligibility or record reasons for screening failure, as applicable.

Subjects who experience any serious or severe TEAEs, or any event of concern should be instructed to contact the study site and be scheduled for a visit for further evaluation. If an unscheduled visit occurs, the reason for the visit and data collected during the visit should be recorded and entered into the unscheduled eCRF.

8.1 Safety Assessment

The safety of the bivalent GI.1 and GII.4 vaccines will be evaluated through the reporting of Solicited Symptoms of Reactogenicity (GI and systemic) for 1 week following the study drug dose and through reporting of frequency, duration, and severity of unsolicited AEs for the next 28 days following the study drug dose. The subjects will then enter the Follow-Up Period after Day 29 and will be monitored for SAEs, AESIs, and NOCIs through Day 365 (Month 12) for safety and duration of immune response. Each SAE, AESI, and NOCI occurrence must be assessed for causality.

AESIs are listed in [Appendix 5](#), the occurrence of these events should be reported to the Sponsor in an expedited manner, similar to SAEs as described in [Section 9](#).

Planned time points for all safety assessments are provided in the SoA ([Table 1](#))

